9.4. Data Sources

This study will use data from secondary population-based healthcare databases reflecting electronic health records or insurance claims related to healthcare encounters. All data sources will have the ability to provide high-quality data on ABRYSVO vaccines (product types and dates), outcomes (diagnoses, procedures, and treatments), and important covariates. It is not currently known the extent to which the ABRYSVO vaccine and product types will be captured in data sources. At the proposal stage for this study, members of VAC4EU were offered the option to participate in the study based on study requirements (https://vac4eu.org/). Several data sources have indicated the ability to participate in the study and are described in the following subsections.

Data availability for each institution may be affected by third parties or external circumstances that are independent from the institution involved in the study as described below in Sections 9.4.1 to 9.4.5

9.4.1. CPRD Aurum (UK)

The CPRD collates the electronic medical records from a network of primary care general practitioners (GPs) in the UK who act as the gatekeepers of healthcare and maintain subjects' life-long medical history and records.⁴⁵⁻⁴⁷ The Aurum dataset, based on practices employing the EMIS electronic medical record software, sources data from over 1,700 primary care practices and includes 47 million patients, of whom 16 million are currently registered and active.⁴⁸ GPs act as the first point of contact for any non-emergency health-related issues, which may then be managed within primary care and/or referred to secondary care, as necessary. Secondary care teams also provide feedback information to GPs about their patients, including key diagnoses. The data in the CPRD are updated approximately quarterly and include demographic information, prescription details, clinical events, preventive care, specialist referrals, hospital admissions, and major outcomes, including death.⁴⁶ Electronic health data are coded by GPs using Read 2, SNOMED and local EMIS codes, and available in CPRD as MEDCODEIDs and PRODCODEIDs. Data include demographics, all GP/healthcare professional consultations, diagnoses and symptoms, results from laboratory tests, information about treatments (including prescriptions), data on referrals to other care providers, hospital discharge summaries (date and diagnostic Read/SNOMED/EMIS codes), hospital clinic summaries, preventive treatment and immunisations, and death (date and cause). Lag time for CPRD Aurum is usually approximately 1-3 months, although this may be extended due to CPRD database technical updates. Linkage of the CPRD primary care data with other subject-level datasets is available for English practices within CPRD Aurum that have consented to participate in the linkage scheme. These linkages include the Hospital Episode Statistics (HES) database, which contains details of all admissions to National Health System (NHS) hospitals in England (Admitted Patient Care,). The availability of

PFIZER CONFIDENTIAL

CT24-WI-GL02-RF02 5.0 Non-Interventional Study Protocol Template For Secondary Data Collection Study 01-Aug-2023 Page 36 of 72 linkage to HES from CPRD Aurum is approximately 66% which equates to approximately 46.8 million individuals. Not all subjects in CPRD Aurum have linked data (e.g., if they live outside of England, if their GP has not agreed that their data may be used in this way). As with standard CPRD subjects, HES data are limited to subjects with research-standard data. The CPRD records are linked to the HES using a combination of the subject's NHS number, sex, and date of birth.⁴⁵ Additional CPRD-linked datasets include Death Registration data from the Office for National Statistics, which includes information on the official date and causes of death (using ICD codes), the CPRD Aurum Ethnicity Record and the Index of Multiple Deprivation (IMD) patient or practice level linked datasets

CPRD is listed under the ENCePP resources database, and access will be provided by the DSRU.

9.4.2. VID (ES)

The VID is a set of population-wide electronic databases covering residents of the Valencia region in Spain, representing approximately 5 million individuals⁴⁹. All the information in the VID databases can be linked at the individual level through a unique personal identifier. The datasets in the VID are as follows:

- The Population Information System (SIP) provides basic information on health system coverage (e.g., dates and causes of Valencia health system entitlement or disentitlement, insurance modality, pharmaceutical copayment status, assigned healthcare department) as well as sociodemographic data (e.g., sex, date of birth, nationality, employment status, geographic location). SIP also includes the date of death captured from the Mortality Registry. The SIP database is the source of the unique patient identifier (the SIP number), which is then used to link health data across different healthcare data sources for Valencia.
- The Ambulatory Medical Record (ABUCASIS) is the electronic medical record for primary and specialist outpatient activity capturing 96% of the population since 2009. The two main database modules are: the Ambulatory Information System (SIA) and the Pharmaceutical Module (GAIA), including paediatric and adult primary care, mental healthcare, prenatal care, and specialist outpatient services, as well as the dates, visits, procedures, laboratory test results, diagnoses, and clinical and lifestyle information. It also includes information on several health programs (e.g., vaccination, healthy children, pregnancy, notifiable diseases), the primary care nurse clinical record, and the health-related social assistance record. The SIA module uses ICD-9-CM for coding diagnoses and, partially ICD-10-ES for data from 2019 onwards.
 - The SIA module also uses the Clinical Risk Groups system to stratify the morbidity of the entire population.
 - The GAIA Pharmaceutical module stores data on all outpatient pharmaceutical prescriptions and dispensings, including both primary care and outpatient hospital departments, using the ATC classification system and the

PFIZER CONFIDENTIAL

CT24-WI-GL02-RF02 5.0 Non-Interventional Study Protocol Template For Secondary Data Collection Study 01-Aug-2023 Page 37 of 72 National Pharmaceutical Catalogue, which allow the identification of the exact content of each dispensing. GAIA does not include in-hospital medication or medication administered in the Accident and Emergency Department (AED). GAIA provides detailed information on prescriptions issued by physicians, such as the duration of treatment and dosage.

- The Hospital Medical Record (ORION) provides comprehensive information covering all areas of hospital-based specialist care, from admission, outpatient consultations, inpatient, emergencies, diagnostic services (e.g., laboratory tests, imaging, microbiology, pathology), pharmacy, surgery, critical care, prevention and safety, social work, at-home hospitalisation, and day-hospitalisation. ORION is currently in the process of being integrated for the whole region, with several databases already fully integrated and available for all hospitals, including the Minimum Basic Data Set at Hospital Discharge (MBDS) and the AED clinical record.
 - The MBDS is a synopsis of clinical and administrative information on all hospital admissions and major ambulatory surgery in the Valencia health system hospitals, including public-private partnership hospitals (approximately 450,000 admissions per year in the region). The MBDS includes admission and discharge dates, age, sex, geographic area and zone of residence, main diagnosis at discharge, up to 30 secondary diagnoses (comorbidities or complications), clinical procedures performed during the hospital episode, and the diagnosis-related group(s) assigned at discharge. The MBDS currently uses ICD-10-ES coding system. Since 2015, MBDS has also included a "present on admission" diagnosis marker and information on tumour morphology.
 - The AED clinical record was launched in 2008 and collects triage data, diagnoses, tests, and procedures performed in public emergency departments. As with the MBDS, the current coding system is ICD-10-ES. Diagnosis codification was approximately of all emergency visits 75% in 2017.

Data on vaccine exposure may be obtained from the VID, which includes information on vaccine type, manufacturer, number of doses, location and administration date, adverse reactions related to vaccines, and if applicable, risk groups. Information in the VID is updated daily. All databases included in the VID are updated frequently (every 1 to 3 months), except the MBDS database, which is updated every 6 months.

9.4.3. SIDIAP (ES)

SIDIAP was created in 2010 by the Catalan Health Institute and the IDIAPJGol Institute.⁵⁰ The database captures healthcare data collected since January 2006 during routine visits from 278 primary care centres linked to the Catalan Health Institute in Catalonia (northeastern Spain). Overall, SIDIAP covers 5.8 million people and is highly representative of the Catalan population (80%). The pseudo-anonymized health data held within SIDIAP originate from, or are linked to, various sources:

PFIZER CONFIDENTIAL CT24-WI-GL02-RF02 5.0 Non-Interventional Study Protocol Template For Secondary Data Collection Study 01-Aug-2023 Page 38 of 72

- ECAP (electronic health records in PHC of Catalan Health Institute) including comprehensive demographic information, clinical and referral events (with diagnoses captured as ICD-10 codes) registered by primary care health professionals (e.g., GPs, paediatricians, and nurses) and administrative staff in the primary care EHRs, vital signs (height, weight, body mass index, blood pressure), primary care laboratory test results, drug prescriptions issued in the PHC (captured as ATC codes), sickness leave and date of death.
- Pharmacy invoice data corresponding to the PHC drug prescriptions
- Database of diagnoses at hospital discharge

Linkages to the hospital discharge database occur on a project-by-project basis. SIDIAP includes all routine childhood and adult immunizations, including the antigen and the number of administered doses.

The SIDIAP database is updated twice per year, in January and July. The SIDIAP data have been shown to fit-for-use for epidemiological research, specifically within VAC4EU projects with respect to the characterization of use for vaccine coverage, benefits, and risk assessments.⁵⁰

9.4.4. EpiChron (ES)

In 2005 the EpiChron Research Group on Chronic Diseases established the EpiChron Cohort Study which used the computerized medical records of patients living in Aragon, a region of north-eastern Spain, to study chronic diseases and multi-morbidities.⁵¹ The cohort was originally approved by the Clinical Research Ethics Committee of Aragon (CEICA). Both cross-sectional and longitudinal studies on multi-morbidity and comorbidity of major index chronic diseases, as well as pharmaco-epidemiological studies, were completed to identify causal relationships among risk factors, diseases and drugs, development of chronic diseases and multimorbidity, and the incidence of adverse health outcomes.⁵¹ The EpiChron cohort was subsequently extended to enable additional research including the safety of COVID-19 vaccines.

The EpiChron Cohort Study now links socio-demographic and clinical anonymized information for the inhabitants of Aragon region, and it is built from the platform of healthcare big data of Aragon (BIGAN). The BIGAN platform integrates a technical infrastructure and a data lake gathering individual data from the regional health service information systems, including primary care, specialized care, hospitalisations, emergency room episodes, drug prescriptions, image diagnosis, laboratory tests, diagnostics, vaccination, medical history and demographics from the users of the public health system of Aragon. This includes about 2 million individuals with historic data, and an active population of 1.3 million individuals.

Within the data lake individual data streams are linked at the individual patient level based on a unique patient health identifier. Diagnoses are coded initially according to the ICPC or ICD coding systems and are subsequently grouped into diagnostic clusters, if needed, using open software (i.e, Clinical Classifications Software). Drug prescriptions and dispensations, including for vaccines, are coded according to the WHO ATC classification system.

PFIZER CONFIDENTIAL CT24-WI-GL02-RF02 5.0 Non-Interventional Study Protocol Template For Secondary Data Collection Study 01-Aug-2023 Page 39 of 72

9.4.5. SNDS (FR)

The SNDS is the French nationwide healthcare database. It currently covers the overall French population (about 67 million persons) from birth (or immigration) to death (or emigration), irrespective of changes to a person's occupation or retirement status.⁵² Using a unique pseudonymized identifier, the SNDS merges all reimbursed outpatient claims from all French health care insurance schemes (SNIIRAM database), hospital-discharge summaries from French public and private hospitals (PMSI database), and the national death register.⁵² SNDS captures healthcare data from 2006 onwards and captures information on:

- Socio-demographic characteristics including gender, year of birth, and area of residence. Socioeconomic status can be derived from the presence of CMU-C (which describes full insurance coverage due to low-income status, deprivation index, and a composite indicator that gives information on patient socioeconomic status based on its geographic residence.
- **Death data** including month, year, and cause. However, there may be lags in death dates (e.g., as of January 2024, cause of death data were available to the end of 2020).
- Long-Term Disease registration with diagnoses captured with ICD-10 codes.
- Occupational accidents and diseases.
- **Outpatient reimbursed healthcare expenditures** for visits, medical procedures, nursing acts, physiotherapy, lab tests, dispensed drugs, medical devices, and transports, etc. For each expenditure, associated costs, prescriber, caregiver information (specialty, private/public practice) and the corresponding dates are provided. Indication and results are not available.
- **Inpatients encounters** capturing the primary and associated ICD-10 diagnostic codes from hospital discharge summaries with the date and duration of the hospital stay, the performed medical procedures, and the related costs. Drugs included in the DRG cost are not captured, though newer more expensive ones paid outside of DRG are available.
- Medication dispensed in community outpatient pharmacies recorded as dispensed preparation packs, with dates (prescription and dispensing): drug information includes ATC code, CIP code (French pharmacy coding system), and EPhMRA code; description of packs in number of tablets and strength; the number of packs dispensed; date of prescription and nature of prescriber, date of dispensing, and the dispensing pharmacy (anonymised). Information on underlying medical indication or date of drug injection are not available. Vaccinations are captured within this data file.

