9.7.3.3. Meta-analysis

For both the comparative cohort and SCRI designs, an appropriate random-effects metaanalytic method will be applied to the main estimates from each data source to obtain a combined effect estimate. The heterogeneity across data sources will be checked, and a forest plot will be produced with the data sources and the pooled estimate.

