CT24-WI-GL02-RF02 5.0 Non-Interventional Study Protocol Template For Secondary Data Collection Study 01-Aug-2023 Page 53 of 72 comparative cohort design. Use of the complementary SCRI design, where appropriate, is therefore a strength as this relies upon individuals for which there is a record of vaccination and is not subject to potential misclassification of vaccination status. It is also possible that some outcomes are the result of immunization errors occurring during the administration of ABRYSVO. This information is not collected regularly and will not be accounted for with the current protocol.

Similarly, outcomes are based on coded events captured in the databases and misclassification due to coding errors, or use of sub-optimal algorithms, may lead to misclassification bias. The databases proposed for this study all have access to linked primary and secondary care data to maximize capture of outcomes of interest. In addition, this study proposes to use outcome algorithms from the ACCESS project which have now been widely applied in vaccine safety studies, with additional validation completed in previous studies. To further assess the potential for misclassification, more sensitive and specific algorithm versions can be applied in sensitivity analyses. Differential ascertainment of outcomes is a potential limitation within the comparative cohort design if the vaccinated and unvaccinated populations have different healthcare seeking behaviour which not only influences their probability of vaccination, but also access to care for outcomes. Given this study focuses on populations with chronically managed conditions, differential outcome reporting is not anticipated due to the frequent nature of healthcare encounters in the populations of interest; but differential healthcare seeking behaviour will still be adjusted for (as feasible) through PS-based ATT weighting.

Further, outcome onset is defined by the timing of the healthcare encounter at which the diagnosis is recorded. For outcomes with rapid onset that are serious enough to warrant an interaction with the healthcare system, the date of onset will closely reflect the date of the diagnosis associated healthcare encounter. Some outcomes may have a longer lag period between symptom onset and diagnosis. For these outcomes, sensitivity analyses can be used to explore potential impact of mis-specification of outcome onset.

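### SNDS has no outpatient diagnosis codes, yet section 9.9 vouches for linked primary and secondary care data in every database, and SNDS rates and pooled IRRs carry no caveat

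*Protocol*

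**What the plan says.** Section 9.4.5 lists what SNDS holds. Outpatient reimbursement data are dated records "for visits, medical procedures, nursing acts, physiotherapy, lab tests, dispensed drugs, medical devices, and transports, etc", and of these the protocol says: "Indication and results are not available". The community pharmacy file has the same gap: "Information on underlying medical indication or date of drug injection are not available". ICD-10 diagnoses are described in two places: "Long-Term Disease registration with diagnoses captured with ICD-10 codes", and inpatient encounters "capturing the primary and associated ICD-10 diagnostic codes from hospital discharge summaries". Cause of death is also held. Occupational accidents and diseases are listed, with no coding described.

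The other four sources are described as holding diagnoses made outside hospital: GP-coded diagnoses in CPRD (9.4.1), primary care and specialist outpatient diagnoses in VID (9.4.2), primary care ICD-10 diagnoses in SIDIAP (9.4.3), and ICPC or ICD codes across primary and specialised care in EpiChron (9.4.4).

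Section 9.9 draws no such distinction: "The databases proposed for this study all have access to linked primary and secondary care data to maximize capture of outcomes of interest". Section 9.7.3.3 has a random-effects method "applied to the main estimates from each data source to obtain a combined effect estimate". It plans a heterogeneity check and a forest plot, but gives no rule for leaving a source out of the pool for a particular outcome.

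**The concern.** Table 1 includes outcomes that can be diagnosed and managed without admission, such as Bell's palsy, single organ cutaneous vasculitis, idiopathic thrombocytopenia and arrhythmia. That is a clinical assumption; the protocol does not state it. For such outcomes, a diagnosis-based SNDS rate measures hospital-treated or registered disease, while the other sources can measure disease diagnosed in any setting.

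Three things are at stake.

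- Incidence rates are part of the primary objective (8.2). An SNDS rate reported without qualification would be too low and would not be comparable with the other rates.
- The 12-month prior-outcome exclusion (9.2.2) depends on a recorded diagnosis. In SNDS, disease managed only in outpatient care before index is invisible, so a later admission can count as a new event.
- Section 9.9 does not expect differential outcome reporting, because these patients have frequent healthcare encounters. In SNDS an outpatient encounter leaves no diagnosis, so that reassurance is weaker there.

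**Working it through.** **The text.** Section 9.4.5 gives SNDS outpatient visits, procedures, tests and dispensings with dates but without indication or results. Section 9.9 says every database has linked primary and secondary care data. SNDS does link outpatient claims to hospital discharges, so the sentence is true of linkage. As an assurance of outcome capture it is wrong for SNDS outpatient diagnoses.

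**Effect on rates and power.** Let s be the share of true events that SNDS captures. The documents give no value, so s is an assumption, taken as equal in both cohorts with no false positives. Then observed rate = s × true rate.

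Arrhythmia is the only one of the example outcomes with a figure in Table 2. The plan's figure comes first. With a background of 2,000 per 100,000 person-years and a 365-day window, p0 = 0.02. For IRR 2, p1 = 0.04. With two-sided alpha 0.05 and 80% power:

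n = (1.960 + 0.842)² × (p0 + p1)/(p1 − p0)² = 7.849 × 0.06/0.0004 = 1,177.3, rounded up to 1,178 per cohort. This matches Table 2.

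Now replace p0 and p1 by s·p0 and s·p1, as if the whole sample came from a source with capture share s. Power at 1,178 is Φ(√[1,178 × (s × 0.02)²/(s × 0.06)] − 1.960).

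| s (assumed) | Observed background per 100,000 person-years | n per cohort for IRR 2 | Power at 1,178 per cohort |
|---|---|---|---|
| 1.0 | 2,000 | 1,178 | 80% |
| 0.8 | 1,600 | 1,472 | 71% |
| 0.6 | 1,200 | 1,963 | 58% |
| 0.5 | 1,000 | 2,355 | 51% |
| 0.4 | 800 | 2,944 | 43% |
| 0.2 | 400 | 5,887 | 24% |

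**Effect on the IRR.** Observed IRR = true IRR × s(vaccinated)/s(unvaccinated). With equal s the ratio is 1 and the IRR is unchanged. Unequal capture would matter: 0.5 against 0.4 turns a true IRR of 1 into 0.5/0.4 = 1.25, and the reverse gives 0.80. Nothing in the protocol shows that capture differs by vaccination status.

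**Weight of SNDS.** Population counts from 9.4, in millions: SNDS 67, CPRD active 16, VID 5, SIDIAP 5.8, EpiChron active 1.3. The SNDS share of people is 67/95.1 = 70%. Under-capture reduces its share of events. With equal true rates and full capture elsewhere, SNDS supplies 67s/(67s + 28.1) of events: 33.5/61.6 = 54% at s = 0.5 and 6.7/34.8 = 19% at s = 0.1.

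**The case against.** The protocol leaves room for a better SNDS algorithm. Section 9.3.2.2 builds outcomes from diagnosis, procedure and treatment codes, tailors them to the source and its record provenance, and defers the detail to the SAP. Section 9.6 allows algorithms to differ by database. SNDS holds dated outpatient procedures and dispensings, so proxy algorithms are possible. This stands, and it rules out saying that SNDS can find these outcomes only on admission or registration. It does not remove the point: without indication or results such proxies are non-specific, and none is named.

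The problem would also be partly visible. Section 9.6.2 benchmarks incidence rates between sources and against published estimates. Section 9.7.4 plans narrow and broad algorithms. Section 9.9 names differences in provenance and completeness as a general limitation, and warns of misclassification in the same paragraph as the disputed sentence. So 9.9 does not deny that capture can fail. But none of these safeguards corrects the SNDS statement or says what happens to the pool when the discrepancy appears.

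A reader might go on to infer that SNDS dominates the pooled IRR, or that the IRR is biased. The documents support neither. The 70% is a population share, not a random-effects weight; section 9.4 says that ABRYSVO capture in the sources is not yet known; and heavy under-capture would itself shrink the SNDS contribution. Equal under-capture leaves the IRR unchanged. Dilution through missed prior disease would need an assumed share of recurrent events and an assumed absence of vaccine effect on them.

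**Conclusion.** The point holds in limited form. Section 9.9 is wrong for SNDS as regards outpatient diagnoses, and 9.7.3.3 pools SNDS for every outcome without distinction. For outcomes that can be diagnosed without admission, SNDS incidence rates would be understated by the factor s, illustratively halved at s = 0.5, and the prior-outcome exclusion would miss outpatient-managed disease. The size is unknown: s is not in the documents, and the choice of affected outcomes is a clinical assumption. It also assumes that the eventual SNDS algorithms do not recover these events by proxy. Table 2 is not in error. This is a correction that should be made to keep a primary-objective rate from being misread; it does not show that the comparative estimates are invalid.

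**What to change.** 1. In 9.9, state that SNDS holds no outpatient diagnoses and that coded non-fatal diagnoses there come from hospital stays or Long-Term Disease registration.
2. In 9.3.2, mark for each Table 1 outcome whether SNDS can capture it without admission or registration and, if so, by which proxy.
3. Where it cannot, label SNDS rates as hospital-treated or registered incidence, and note that the prior-outcome exclusion has the same limit.
4. For those outcomes, prespecify in 9.7.3.3 and 9.7.4 a sensitivity analysis giving the pooled IRR with and without SNDS. Add a hospital-only algorithm across sources where linkage allows.

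The cost is wording plus one extra pooled analysis per affected outcome, and the estimate without SNDS will be less precise. The hospital-only run is not free everywhere: HES linkage covers about 66% of CPRD Aurum (9.4.1), and SIDIAP hospital linkage is arranged project by project (9.4.3). That is a reason to keep it as a sensitivity analysis and not make it the main estimate.
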